- **If still interested:** Participants will be sent a link to the on-line consent form. If they failed PAR-Q screening, they will also be sent a link to a RedCap form to consent to allowing study staff to contact their physician and provide physician contact information.
- **If no longer interested:** They will be thanked and asked if they would be willing to be contacted regarding future study opportunities.
- **Attempts to contact:**
 - Study staff will make up to three call attempts to reach potential participants for the orientation call. If they are not reached at this point, staff will follow-up with one last call and email.
 - Study staff will make up to three e-mail attempts to reach potential participants to complete the informed consent. If unable to reach after the third attempt, study staff will call the participant and send one final email. Those who we are unable to reach after these attempts will be marked as “ineligible,” with the reason as “unable to contact.”

Assessments

After completion of informed consent, women will be e-mailed baseline study questionnaires via RedCap and notification that their accelerometer packet has been placed in the mail. The accelerometer packet includes: accelerometer, accelerometer instructions, accelerometer log, printed copy of the informed consent, a self-addressed stamped return envelope to return the accelerometer. Questionnaires will take approximately 30-45 minutes to complete and participants will be asked to complete the on-line study questionnaires within 10 days of receipt. They will be asked to wear the accelerometer for 7 consecutive days starting on the day indicated on the log and mail it back to study investigators at the end of the 7 days period.

Figure 5. Participant Flow Through Study

PROTOCOL TITLE: Designing with Dissemination in Mind: Optimization of a mHealth Physical Activity Intervention for Breast Cancer Survivors (Fit2Thrive)

Women will also have the option to participate in the self-collection of a 2.5 mL blood sample to be collected by pricking their finger with a retractable lancet and placing 5, 50 μ L spots of blood on a sample collection card. They will be mailed all materials needed to collect the blood spot (i.e. lancet, alcohol swab, band-aid) and written instructions with pictures for collecting and returning the sample as well as a self-addressed stamped envelope.

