Exploratory Aim 2. This aim is to explore the relationship between the 5 intervention components and each BC progression (IL-6, IL-10, CRP and TNF α) and cardiometabolic (CRP, BG, TG, TC, HDL-C) biomarker. We will also examine effects on overall risk for each category using composite z-scores. Our hypothesis is a set of components will emerge as most effective for changing each biomarker, but a second set of components, which may not be the same, may emerge as having the greatest composite effect or being most cost-efficient to achieve these outcomes. We will employ an intention-to-treat (ITT) approach by including all participants recruited into the study regardless of compliance. These hypotheses will be tested using intention-to-treat linear mixed model analyses to test differences in outcomes by intervention components. We will also test 2-way interactions between selected intervention components. Because we will use effect (-1,1) coding rather than dummy (0,1) coding, the power for tests to detect main effects and interaction effects are identical for effects of identical size. These data will be used in conjunction with parent study data to determine which intervention components will be tested in a more definitive trial.

11.2 Power Analysis.

Because this is a pilot test to evaluate the feasibility, acceptability, and preliminary efficacy of the different intervention components, sample size planning was determined by resource constraints (vs. a power analysis) for the primary aims.

Dried Blood Spots. To determine if the sample size (n=256) is sufficient to address our

exploratory aim to explore biomarkers obtained via DBS, we conducted a power analysis to calculate the minimal detectable difference (MDD)¹¹⁶ for each biomarker assuming 20% attrition at 24 weeks, an alpha of 0.05, and two-sided testing. The MDD defines the difference that must exist between those with the component “on” vs. “off” to detect a statistically significant effect. We used standard deviations

Table 8. Minimal Detectable Differences

Marker	SD	ICC	Study	MDD
IL-6	1.1	0.80	Jones 2013	0.40 pg/mL
IL-10	3.8	0.80	Rogers 2012	1.37 pg/mL
TNF α	0.6	0.80	Jones 2013	0.21 pg/mL
CRP	2.4	0.44	Jones 2013	0.78 mg/dL
BG	7.8	0.49	Guinan 2013	2.57 mg/dL
HDL-C	0.3	0.87	Fairey 2005	0.11 mmol/L
TG	0.7	0.79	Fairey 2005	0.27 mmol/L
TC	0.3	0.75	Fairey 2005	0.10 mmol/L

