from published BCS PA interventions¹¹⁷ and intra-class correlations (ICC) from [name] prior study,¹¹⁸ if available. Otherwise, a conservative ICC of 0.8 is assumed. Table 8 displays MDDs for component main effects and two-way interactions at 12 and 24 weeks. We have 80% power to detect differences at least equal to between group differences observed in prior intervention studies for all inflammatory^{119,120} and CVD markers^{121,122} except for BG. Given no study has evaluated specific PA intervention component effects on biomarkers in BCS in the context of a MOST design, we accept this limitation.

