Phase 1. Potential subjects will be recruited using IRB-approved e-blast to the Army of Women[®], scripted phone calls and IRB-approved pamphlets/fliers and e-mails.

Phase 2 For survivors, our primary recruitment method will be an e-blast to the Army of Women[®]. If this is not successful, we will post advertisements on on-line forums and distribute fliers at local community organizations and events. Fliers will be posted and handed out to potential participants.

Potential buddy participants will be identified via breast cancer survivor participants and invited to participate in the online screening by study staff.

Potential post-intervention interview participants will be identified by the study team and invited to participate in the interview by study staff via email.

All recruitment materials will be IRB-approved.

22.5 Payments to subjects.

Phase 1. Survivors will be paid \$15.00 via Amazon.com e-gift card following participation in the interview session. Experts and community partners will be paid \$20.00 via an Amazon.com e-gift card following participation in each interview session. Survivors will be paid \$10.00 via an Amazon.com e-giftcard for each app development session (up to 2) and another \$20.00 via an Amazon.com e-giftcard for the field test.

Phase 2. Survivors will be paid \$20.00 via check following completion of baseline, 12 week and 24 week follow-up assessments (on-line questionnaires and accelerometer). If they only complete one aspect of the assessment (i.e. wear the accelerometer or answer questionnaires), their pay will be pro-rated to \$10 for each component completed. Women who choose to participate in the optional blood sample collection will receive a \$15.00 check after receipt of their sample at each of the three time points.

“Buddies” who agree to complete the optional baseline, 12 week and 24 week on-line questionnaire assessments, and complete at least two assessments, will get to keep the Fitbit (\$60 value). Those who do not complete at least two assessments will be asked to mail the Fitbit back to the study team.

Participants who agree to participate in post-intervention interviews will be paid \$20.00 via Amazon.com e-gift card for participation in this portion of the study.

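### The dried-blood-spot power statement takes 20% attrition as the only loss for an optional sample, and Table 8 does not say which visit or average its detectable differences refer to

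*Combined protocol and SAP*

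**What the plan says.** Section 11.2 introduces the biomarker calculation with "To determine if the sample size (n=256) is sufficient to address our" exploratory biomarker aim. Minimal detectable differences (MDDs) are computed "for each biomarker assuming 20% attrition at 24 weeks, an alpha of 0.05, and two-sided testing". Each MDD is defined as a difference between women with a component on and women with it off. On timing the text says only: "Table 8 displays MDDs for component main effects and two-way interactions at 12 and 24 weeks". Table 8 prints one MDD per marker. The conclusion is "We have 80% power to detect differences at least equal to between group differences observed in prior intervention studies for all inflammatory" and cardiovascular markers, with glucose (BG) as the exception.

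Other sections bear on how many samples there will be:
- Section 9.2 (Assessments): "Women will also have the option to participate in the self-collection" of blood. Section 22.5 likewise refers to "Women who choose to participate in the optional blood sample collection".
- Section 3.2 lists exclusions that apply only to blood collection: a prior cardiovascular event, and immune or endocrine conditions.
- Section 2.2 cites at least 90% adequacy for self-collected samples.
- Sections 4.0 and 23.1 expect 80% of buddies (102 of 128) to agree to their own optional questionnaires.

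Section 11.1, Exploratory Aim 2, plans "intention-to-treat linear mixed model analyses to test differences in outcomes by intervention components", "including all participants recruited into the study regardless of compliance".

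**The concern.** The power calculation starts from all 256 Phase 2 women, but only those who opt in, pass the blood-only exclusions and return a usable card can contribute. Section 11.2 gives no uptake, no blood-only exclusion rate and no usable fraction, although the plan does discount the buddies' optional questionnaires.

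Table 8 is the only numerical support for n=256 in Exploratory Aim 2. Section 11.1 says the biomarker results, together with the parent-study data, will help choose components for a more definitive trial. If sensitivity is overstated, a component with no visible biomarker effect looks more firmly excluded than it is. Without the time contrast, a reader also cannot tell whether a printed MDD applies at week 12, at week 24 or to their average.

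**Working it through.** **Inputs.** From Section 11.2 and Table 8: n=256, 20% attrition at 24 weeks, two-sided alpha 0.05, 80% power, and the SD, ICC and MDD of each marker. Allocation is taken as 128 on and 128 off per component, as the balanced factorial in Table 7 implies. The multiplier is 1.960 + 0.842 = 2.802. Week-12 attrition and blood uptake are not in the documents; values below are assumptions.

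**1. Is Table 8 a single-visit contrast?** Unadjusted, with no dropout, MDD = 2.802 × SD × √(2/128).
- CRP (SD 2.4): 0.84, against 0.78 printed.
- BG (SD 7.8): 2.73, against 2.57 printed.

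Even the lowest SDs that round to 2.4 and 7.8 give 0.823 and 2.714. These two rows cannot be unadjusted single-visit values. A check that does not depend on n agrees: the BG to IL-10 ratio of MDD/SD is 0.3295/0.3605 = 0.914. A two-visit average predicts √(1.49/1.80) = 0.910, and any unadjusted single visit predicts 1.00. At 24 weeks, change-score and baseline-adjusted forms miss widely (IL-6 0.27 and 0.26, against 0.40).

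**2. Reproducing Table 8.** Take the equal-weight average of weeks 12 and 24, with retention p1 and p2 and base N:

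MDD = 2 × 2.802 × SD × √(V/N), V = 0.25 × [1/p1 + 1/p2 + 2·ICC/√(p1·p2)].

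With N=256, p1=0.90 (assumed) and p2=0.80:

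| Marker | Computed | Printed |
|---|---|---|
| IL-6 | 0.397 | 0.40 |
| IL-10 | 1.371 | 1.37 |
| TNFα | 0.217 | 0.21 |
| CRP | 0.775 | 0.78 |
| BG | 2.561 | 2.57 |
| HDL-C | 0.110 | 0.11 |
| TG | 0.252 | 0.27 |
| TC | 0.107 | 0.10 |

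TNFα, TG and TC are off by 3–7%, which rounding of the one-decimal SDs can explain.

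**3. How much sample loss could Table 8 already contain?** Solve N = (2 × 2.802 × SD/MDD)² × V for each row, let SD, ICC and MDD vary within rounding, and keep the N that fit all eight rows.
- Equal weights, week-12 attrition 0, 10 and 20%: N = 237–247, 249–259 and 264–275.
- Maximum-likelihood average, V = 1/[2·p2/(1+ICC) + (p1 − p2)], no week-12 dropout: N = 223–230.

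The base therefore lies between about 223 and 275, depending on week-12 attrition and weighting. The lowest value leaves 1 − 223/256 = 13% for losses beyond attrition. That covers a 10% unusable fraction plus about 3% non-uptake (0.871/0.90 = 0.968), and no more.

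**4. Size.** If the usable sample is a fraction f of what Table 8 assumes, power at the printed MDD = Φ(2.802·√f − 1.960), and the MDD grows by 1/√f. Women with usable 24-week blood = 256 × 0.80 × uptake × 0.90, against 205 with attrition alone.

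| Assumed uptake | Women, week 24 | Power, no such loss in Table 8 (f = 0.90 × uptake) | MDD factor | Power, 10% loss already in Table 8 (f = uptake) |
|---|---|---|---|---|
| 100% | 184 | 76% | 1.05 | 80% |
| 90% | 166 | 71% | 1.11 | 76% |
| 80% | 147 | 66% | 1.18 | 71% |
| 70% | 129 | 60% | 1.26 | 65% |
| 50% | 92 | 47% | 1.49 | 51% |

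The MDD factor goes with the no-loss column.

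**The case against.** The strongest reply is that the 80% sentence concerns prior-study differences, not the MDDs. If those differences exceed the MDDs by a margin, the sentence survives incomplete uptake. This stands: the percentages above are power at the printed MDDs, and a reader who infers that the 80% claim is false goes further than the documents allow.

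Second, a 20% allowance may already include unusable samples. In the earlier study described in Section 2.2, 370 of 442 women (83.7%) had valid follow-up accelerometer data, and the reasons for missing data included malfunction, loss in the mail and insufficient wear. This also stands, which is why both power columns are shown. It does not dispose of the point, because the most Table 8 can hold is about 13%.

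Third, a reader might infer that Table 8 is miscalculated, or that it needs full uptake and fully usable samples. Neither follows. The table is approximately reproducible, and its base cannot be pinned to 256 without the week-12 attrition. Nor is the contrast wholly missing: the on-versus-off comparison is stated, and only its timing is not.

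Fourth, the intention-to-treat sentence could be read as claiming biomarker results for women who never gave blood. Because the same paragraph sets its data beside those of the parent study, the women it refers to may be those in the blood component. It needs clarifying and is not a demonstrated error.

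Finally, the buddies' 80% concerns other people and questionnaires. It is a yardstick, not evidence of blood uptake.

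**Conclusion.** The point holds as an unsupported power statement and an incomplete specification. Section 11.2 judges n=256 without allowing for opt-in, blood-only exclusions or unusable samples, and it omits the time contrast and week-12 attrition needed to interpret Table 8. At full uptake, power at the printed MDDs is 76% to 80%, depending on whether a 10% loss is already in the table; at 80% uptake it is 66% to 71%, and at 50% it is 47% to 51%. These figures assume a normal approximation, 1:1 allocation, 90% usable samples and uptake values that the documents do not give. The two-visit average is inferred from the numbers.

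The weight is low. The aim is exploratory, Section 1.1 describes the samples as collected for future research, and resource limits rather than power set the sample size for the primary aims.

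**What to change.** In Section 11.2:
- Recompute Table 8 for an expected n of 256 × uptake (after the blood-only exclusions) × usable fraction × retention, over a stated range such as 50–100% uptake. Say whether the 20% includes unusable samples.
- For each MDD, state whether it is a week-12, week-24 or averaged contrast, the week-12 attrition assumed, and whether it is baseline-adjusted, so that it matches the mixed model in Section 11.1.
- Print the prior-study differences and re-check the 80% sentence against the restated MDDs, or withdraw it.

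In Section 11.1, Exploratory Aim 2, clarify that the biomarker analysis takes women who opted in to blood collection, as randomised, with all available samples. State how any opt-in after randomisation is handled, since Section 9.2 repeats the same procedures at 12 and 24 weeks.

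The cost is recalculation and wording, with no extra enrolment. The plan has to commit to an expected uptake, and the stated power will probably look less favourable.

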11.3 Data Security

Each participant will be randomly assigned an identification number to ensure confidentiality of data. This will be the only way of matching data with a specific person. Nitro Study Tracker will be the only place where the ID will appear with the participant’s name in the present study. This database will only be accessible by the investigators.

PROTOCOL TITLE: Designing with Dissemination in Mind: Optimization of a mHealth Physical Activity Intervention for Breast Cancer Survivors (Fit2Thrive)

This electronic database will house participant contact information and is stored on a secured, password-protected network, accessible only by the investigators.

To ensure the integrity of the data collected from study participants several procedures will be implemented. All personnel involved in data collection will be thoroughly trained in all assessment methods thus ensuring consistent applications of procedures and measurement consistency across participants. All data will be automatically saved in the secured, password protected RedCap system and will be downloaded to a password protected network folder protected ensuring access only by the investigators. Any hard copies of data will only include the participants ID number and will be entered into the RedCap system only using this ID number. All raw data will be de-identified (with the exception of the study ID number). These data will be saved to a portable hard drive which will be stored in a locked cabinet in the PI's laboratory. Any hard copies of data will be stored in a separate, locked cabinet from the informed consents in the PI's laboratory. Files containing identifying information obtained for purposes of tracking participants and monitoring of subject payments are kept in a locked file in a locked office separate from study related data. Data will only be linked to identifying information through a study ID. Under no circumstances will individually identifiable data be released to anyone without the written consent of the subject. Results will be reported as group findings only. In the past we have found that all of these procedures are effective at reducing risk for study participants.

Issues related to data integrity will be discussed on a weekly basis as a recurring agenda item in the weekly project meeting to ensure constant monitoring of our data integrity. Only the investigators will have access to participant data. All staff with access to the data will have completed Northwestern University requirements for the responsible conduct of research including the Collaborative Institutional Training Initiative (CITI) Training Modules.

11.4 Quality Control of Collected Data

Given that the majority of data will either be recorded electronically, entered electronically by participants or collected electronically via accelerometers or cellphones, we anticipate limited issues with quality control. However, all hard copy data that is entered by study staff will be double entered and checked to ensure data integrity. Additionally, all data will be checked for missing data and erroneous data by examining descriptive statistics and score ranges of all variables. Subsequently, all data will be examined for violation of basic statistical assumptions (i.e., normality, multicollinearity, and homoscedascity) and transformed if necessary. In order to ensure data are missing at random, we will compare participants who have data on a given variable to those who do not on demographic and disease characteristics to ensure there is no pattern to the missingness.

11.5 Specimen Handling

Blood specimens will be self-collected by participants in their homes and mailed back to [name] using the U.S. Postal Service for analysis and storage for future use which may include analysis of biomarkers of BC progression and CVD risk, whole genome sequencing, and epigenetic profiling. Everyone handling the blood products will receive Bloodborne Pathogens Training. As described above,

PROTOCOL TITLE: Designing with Dissemination in Mind: Optimization of a mHealth Physical Activity Intervention for Breast Cancer Survivors (Fit2Thrive)

specimens will not be stored linked to direct identifiers (only by ID number). Specimens will be accessible by [name] and co-investigators with IRB approval.

12.0 Provisions to Monitor the Data to Ensure the Safety of Subjects

N/A as this study involves only Minimal Risk to subjects.

13.0 Withdrawal of Subjects

13.1 Procedures for early termination.

Participants may withdraw from either Phase 1 or Phase 2 of the study at any time.

Procedures specific to Phase 2. For any participant who elects to withdraw, permission will be sought to continue to collect outcome data for use in the analysis. However, all participants in the intervention will be accounted for in all follow-up analyses following the intent-to-treat principle. If participants withdraw from the study, and do not agree to return for follow-up assessments, data from their most recent assessment will be carried forward and imputed in subsequent assessment points (Last Observation Carried Forward).

13.2 Procedures to follow when subjects withdraw from research.

Participants may withdraw from the study at any time during Phase 1 or Phase 2. For phase 2, permission will be sought to continue to collect outcome data for use in the analysis.

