The purpose of the present study is to apply the Multiphase Optimization Strategy (MOST)²⁵ to develop and pilot test a set of mobile health (mHealth) PA intervention components for breast cancer survivors that are targeted at social cognitive constructs known to impact PA uptake and designed with D&I in mind from the outset. MOST is an innovative multi-phase framework adapted from engineering that uses highly efficient factorial experiments to evaluate the individual and combined effect of intervention components. The present study will use a MOST approach to examine the effect of PA intervention components that vary on cost. These data will be used to assemble an intervention to be evaluated in a larger R01 that is optimized to yield the maximum increase in PA for the minimum cost. The proposed study represents the first systematic effort to use MOST to design a highly disseminable PA intervention for breast cancer survivors. The resulting intervention will have great potential for scalability because it engages relevant stakeholders (i.e. survivors, experts, community leaders) in the design, uses technology (smartphones) participants already own, requires no on-site visits, and recruits using the Army of Women,[©] a national breast cancer research registry the PI successfully used previously.

Specific Aims:

Aim #1. Use a patient-centered approach to select a set of five PA intervention components for breast cancer survivors designed to impact social cognitive constructs. Although we have identified candidate app/intervention components, selection of which ones to test will be made based on consensus between investigators and relevant stakeholders including survivors, experts and community leaders (n=10 of each). Survivors (n=10-20) will also be involved in iterative testing to determine app usability and functionality.

Aim #2. Pilot test the feasibility and acceptability of candidate intervention components in a 12-week MOST experiment. A highly efficient experimental design will be used for this pilot study of survivors (n=256). Feasibility will be assessed by a) intervention reach, b) participant retention, and c) adherence to the intervention protocol. Acceptability will be assessed by ratings of the acceptability and usefulness of intervention components.

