Aim#3. Examine effects of the intervention components on PA. The effect of the intervention components on changes in accelerometer measured PA (minutes/week) at 12 weeks and 24 week follow-up will be examined using a highly efficient experimental strategy powered to detect effects of individual components.

Exploratory Aim. Examine potential effects of the intervention components on important patient-reported outcomes (PROs). We will examine the effect of each intervention component on changes in physical function, fatigue, depression and QOL at 12 weeks and 24 week follow-up using well-validated self-report measures.

Exploratory Aim 2. Examine the effects of the 5 intervention components on biomarkers of breast cancer (BC) progression and cardiovascular disease (CVD) risk in a 12 week intervention. We will collect blood samples for future research to examine evaluate the extent to which each intervention component ameliorates a pro-inflammatory phenotype associated with BC progression and CVD risk (i.e. interleukin-6, tumor necrosis factor-alpha interleukin-10, c-reactive protein) and cardiometabolic biomarkers (i.e. glucose, triglycerides, total cholesterol and high-density lipoproteins).

1.2 Hypotheses to be tested.

Aim #1. We hypothesize that a set of 5 components will emerge as favored by participants and approved by experts and investigators.

Aim #2. The primary hypotheses are: a) 75% of eligible survivors will agree to participate in the intervention; (b) enrollees will demonstrate engagement by monitoring PA on >80% of the study days and using one or more additional app components at least weekly. Descriptive analyses (means, frequencies) will be used to describe these results

Aim#3 and Exploratory Aim #1 and #2. Our hypothesis is that a set of components will emerge as most effective for increasing PA and minimizing cost but a additional

PROTOCOL TITLE: Designing with Dissemination in Mind: Optimization of a mHealth Physical Activity Intervention for Breast Cancer Survivors (Fit2Thrive)

configurations of intervention component may emerge as having the largest, most cost-efficient impact on PROs, biomarkers of BC progression and CVD risk .

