Aim 3 and Exploratory Aim 1. These aims are to determine the preliminary effectiveness of intervention components on minutes of accelerometer-measured moderate and vigorous PA (Aim 3) and PROs (physical function, fatigue, depression, QOL; Exploratory Aim). Our hypothesis is that a set of components will emerge as most effective for increasing PA and minimizing cost, but a second set of intervention component may emerge as having the largest, most cost-efficient impact on PROs. These hypotheses will be tested using intention-to-treat mixed linear model analyses to test differences in outcomes by intervention components. The study was not designed to have statistical power to detect differences over time with inferential tests. If descriptive statistics suggest that the intervention (a) is feasible and acceptable and (b) seems likely to increase PA, we will plan a future randomized controlled trial with sufficient power (>.80) to detect clinically-meaningful effects in this population. If we fail to achieve certain benchmarks for

PROTOCOL TITLE: Designing with Dissemination in Mind: Optimization of a mHealth Physical Activity Intervention for Breast Cancer Survivors (Fit2Thrive)

feasibility, acceptability, or safety, we will refine the protocol as needed prior to proceeding.

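### Section 13.1's last-observation-carried-forward rule, which most naturally reaches the component-effect mixed models, can distort the 12- and 24-week estimates, though probably by little

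*Combined protocol and SAP*

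**What the plan says.** Section 13.1 (Procedures for early termination) deals with Phase 2 withdrawals in three steps.

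- On withdrawal, "permission will be sought to continue to collect outcome data for use in the analysis".
- Next, "all participants in the intervention will be accounted for in all follow-up analyses following the intent-to-treat principle".
- Then, for women who withdraw and do not agree to follow-up assessments, "data from their most recent assessment will be carried forward and imputed in subsequent assessment points (Last Observation Carried Forward"), abbreviated LOCF below.

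Section 11.1 gives the analysis. For Aim 3 and Exploratory Aim 1: "These hypotheses will be tested using intention-to-treat mixed linear model analyses to test differences in outcomes by intervention components". For Exploratory Aim 2 (biomarkers) the sentence is almost the same: "These hypotheses will be tested using intention-to-treat linear mixed model analyses to test differences in outcomes by intervention components". Neither paragraph says how missing values are handled. The text introducing Table 7 says that all 256 women enter every effect estimate.

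Table 6 schedules the accelerometer at baseline, 12 and 24 weeks only. Under Follow-up in Section 9.2, regular staff contact ends at week 12.

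**The concern.** A single carried-forward value is treated as if it had been observed, and here the design makes that value doubtful. Every woman receives a core programme meant to raise PA. A woman who leaves before week 12 has only her baseline accelerometer value, so LOCF records zero gain for her at both later visits. A woman who leaves after week 12 has that value repeated at week 24, so LOCF records full maintenance over a period in which staff contact has stopped.

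In Aim 3, "changes in accelerometer measured PA (minutes/week) at 12 weeks and 24 week follow-up will be examined", and of the study's results Section 1.1 says: "These data will be used to assemble an intervention to be evaluated in a larger R01". Section 11.1 adds that "The study was not designed to have statistical power to detect differences over time with inferential tests". The size and ordering of the five component estimates therefore matter more than the tests, and LOCF acts directly on the estimates. A likelihood-based mixed model needs no filled values: it uses every observed visit and is valid if the data are missing at random.

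**Working it through.** **Does LOCF reach the models?** Section 13.1 covers all follow-up analyses under intent-to-treat and states LOCF in the next sentence. Section 11.1 labels the mixed models intention-to-treat, and no section exempts them or gives a different rule. This is an inference, but it is the natural reading.

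**Inputs.** From the documents: 256 women, hence about 128 with each component on and 128 off, and the visit schedule. The documents attach no figure to LOCF, so there is none to reproduce. Assumed, in min/week: component effects D12 and D24, gain m at week 12 without the component, SD, and correlation r between visits. Let e and l be the shares filled because of early (before week 12) and late withdrawal.

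**Equal, random drop-out.**

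- Week 12: expected LOCF effect = (1-e)(m+D12) - (1-e)m = (1-e)D12, so bias = -e·D12.
- Week 24: expected LOCF effect = (1-e-l)D24 + l·D12, so bias = -e·D24 + l(D12-D24).

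| D12, D24 | e, l | LOCF, week 12 | LOCF, week 24 |
|---|---|---|---|
| 30, 30 | 1%, 0% | 29.7 | 29.7 |
| 30, 30 | 4%, 4% | 28.8 | 28.8 |
| 30, 30 | 10%, 10% | 27 | 27 |
| 30, 0 | 10%, 10% | 27 | 0.1×30 = 3 |
| 60, 30 | 10%, 10% | 54 | 0.8×30 + 0.1×60 = 30 |

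A simulation agrees (random-intercept REML, baseline as a response with equal baseline means, SD 90, r = 0.5, 4,000 replicates). For constant 30 at 10%/10%, the observed-data model gives 29.9 and 30.1 at the two visits, and LOCF gives 26.8 and 27.1. For 30 falling to 0, the week-24 estimates are 0.2 and 3.2.

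**Scale.** The baseline-adjusted SE of one component effect with complete data is SD×√(1-r²)×2/16. With SD 90 and r = 0.5 this is 9.7; with SD 60 and r = 0.6 it is 6.0. A bias of 0.3 is then 0.03 to 0.05 SE, and a bias of 3 is 0.3 to 0.5 SE.

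**Unequal early drop-out, component with no effect.** Week-12 bias = (e_off - e_on)×m. For 4% on and 6% off, it is +0.6 (m = 30) to +1.2 (m = 60). For 5% on and 20% off, it is +4.5 to +9. Reversing the imbalance reverses the sign.

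**How many women might be filled?** Section 2.2 reports a prior study with 442 valid accelerometer records at baseline, of whom 370 also had valid data at six months, so 72 (16.3%) were lost. The follow-up reasons listed are not worn 40, insufficient wear 17, malfunction 5 and lost 5, together 67. Withdrawal is not listed. If only the unexplained 72-67 = 5 were withdrawals, the share is 5/442 = 1.1%. If every non-wearer was also a withdrawal, it is 45/442 = 10.2%. That was a prospective study, not this intervention, so the range is only a guide.

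**If withdrawers return to baseline (constant effect 30, week 24).** The truth is 0.8×30 = 24 in each row.

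| e, l | Truth | Observed-data model | LOCF |
|---|---|---|---|
| 20%, 0% | 24 | 30 | 24 |
| 10%, 10% | 24 | 30 | 27 |
| 0%, 20% | 24 | 30 | 30 |

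**Reported precision (SD 90, r = 0.5, equal-baseline constraint).** At 10%/10% the week-24 SE is 10.8 from observed data and 9.4 under LOCF: 10.8/9.4 = 1.15. At 4%/4% it is 10.1 and 9.6: 10.1/9.6 = 1.05. Without the constraint, the complete-data SE rises from 9.7 to 90×√(2×0.5)×2/16 = 11.25, and the 10%/10% SE rises from 10.8 to 12.2.

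**The case against.** The strongest reply has four parts.

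1. *Scope.* A reader might say that Section 13.1 expressly orders LOCF into the mixed models. It does not: the LOCF sentence names no analysis and Section 11.1 names no imputation. This stands as a limit on the claim. It does not remove the problem, because the text leaves no other rule for these women.
2. *Size.* The rule covers only women who withdraw and also refuse assessment, after permission to continue has been sought. It does not cover non-wear or lost devices. A reader might take the 20% attrition in Section 11.2 as the share filled, but that is a biomarker planning figure for attrition and not a refusal rate. A reader might also stress unequal drop-out. In the simulation, 5% early and 5% late with the component on, against 20% and 10% with it off, makes LOCF reject a true null at week 12 in 17% of trials. Nothing in the documents suggests such an imbalance.
3. *The alternative also rests on an assumption.* If withdrawers return to baseline, LOCF is closer to the truth than the observed-data model, or tied with it, in all three rows above. This stands, and it is why a sensitivity analysis is needed. It does not rescue LOCF as the main rule, because LOCF is wrong for late withdrawers in that case too. Nor can the missing-data comparison in Section 11.4 settle the matter: it is a quality-control check and does not commit the models to missing at random.
4. *Status.* These outcomes are secondary or exploratory in a pilot sized by resources. This limits the severity.

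**Conclusion.** The point holds in a limited form. Read with Section 11.1, Section 13.1 most naturally puts LOCF values into the component-effect models. There they can shrink a lasting effect, keep a faded one, or favour the component level with fewer early withdrawals. With equal random drop-out and an assumed constant effect of 30 min/week, the bias runs from about -0.3 (1% filled early) to -3 (10%).

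These figures are illustrations and not bounds: a constant effect of 60 with 20% filled early would give -12. They rest on assumed effects and shares filled, and the SE comparisons also rest on an assumed SD and correlation. The prior study's losses suggest that the affected share may be well below 20%. The severity is minor to should-fix: the expected distortion is modest, but the estimates feed the choice of components for the next trial and the correction is cheap.

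**What to change.** Delete LOCF as the analysis rule in Section 13.1. In 13.1, and in 11.1 under Aim 3 and Exploratory Aims 1 and 2, state:

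> Women who withdraw and decline follow-up stay in the analysis through their observed visits. All observed baseline, 12-week and 24-week values enter a likelihood-based (REML) mixed model, with baseline as a response and baseline means constrained equal across component levels. Missing values are not imputed.

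Treating baseline as a response retains women who leave before week 12. Randomisation after the baseline assessments justifies the equal-baseline constraint, and the precision figures above depend on it.

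Add one sensitivity analysis for PA in women who withdrew and refused assessment: multiple imputation under missing at random, then a stated range of downward shifts that includes return to the baseline mean. Report the five component effects at both visits for each shift, because the main model can be too favourable if these women return to baseline.

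The cost is plan wording and one extra analysis, with no new data or participants. Reported week-24 SEs would be about 15% larger if 20% of women were filled and about 5% larger if 8% were, under the assumed inputs and with the constraint.
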